4.11 Statistical Methods

Findings will be reported according to the CONSORT guidelines for cluster randomized trials. Analyses will be intention to treat and include all data from trial children and their families, regardless of their exposure to the radio campaign. Random-effects linear regression models using individual-level data will be used to adjust for the clustered design and any imbalances between intervention and control arms. Effect sizes will be presented as standardized mean differences with 95% confidence intervals (CI). The data analysis plan will be published prior to the end of recruitment.

Analyses will initially be carried out blind with clusters randomly allocated randomly to groups X & Y. Results will be presented to the TSC /DMEC and all data procedures and statistical methods agreed. This is in order to ensure that any decisions made concerning methods, choice of indicators, outliers etc cannot be influenced by the trial results. Partially unblinded analyses will then be presented with the two trial groups labelled by letters rather than as intervention and control. The findings will be discussed, and the interpretation of any differences agreed, ignorant to the knowledge of which group is intervention and which control. The code will then be broken. Interpretation of findings cannot be changed at this stage.

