4.4 Randomisation of clusters

The SUNRISE campaign will be broadcast by the local radio stations in eight of the clusters chosen at random to be in the intervention group; the other 7 clusters will be in the control group and their radio stations will continue to broadcast as normal. This will be carried out using restricted randomization to ensure that the intervention and control clusters are balanced at baseline with respect to radio exposure and predictors of ECD outcomes as follows:

- Mean CREDI z-score; difference between intervention and control groups to be a maximum of 0.1.
- Mean % key FCI behaviours followed by mothers; difference between intervention and control groups to be a maximum of 10%.
- % mothers listening to the radio in the last week; difference between intervention and control groups to be a maximum of 10%.
- % mothers who are literate; difference between intervention and control groups to be a maximum of 10%.

The restricted randomization will be carried out by the independent trial statistician using the cvcrand command¹ in Stata. This performs covariate-constrained randomisation which is suitable for cluster randomised trials with a small number of clusters. The 20% most balanced allocation schemes using the four variables described above will be generated. This subset will then be checked to ensure that it is not a biased selection by checking for anomalies in the frequencies of co-allocations of pairs of clusters. If bias happens, the restricted randomisation will be repeated using the CREDI criteria plus 2 of the other three. One allocation scheme will then be selected at random from the final restricted randomisation results and shared with the campaign team but not with the trial evaluation team.

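### Section 4.11 ties covariate adjustment to observed imbalance, although the randomisation is restricted on predictors of the outcome; adjustment should be fixed in advance, for baseline CREDI at least

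*Protocol*

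**What the plan says.** Protocol section 4.11 specifies random-effects linear regression on individual data, which "will be used to adjust for the clustered design and any imbalances between intervention and control arms".

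Section 4.4 randomises 15 clusters, 8 to the campaign and 7 to control, so that the arms are "balanced at baseline with respect to radio exposure and predictors of ECD outcomes". The four variables are mean CREDI z-score, key FCI behaviours, radio listening in the last week and maternal literacy. "The 20% most balanced allocation schemes using the four variables described above will be generated". If the retained set looks biased, the restriction is repeated with CREDI and two of the other three, so CREDI is the one variable that is always kept.

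Section 4.11 also sets a sequence. "Analyses will initially be carried out blind with clusters randomly allocated randomly to groups X & Y"; on those results the committees see "all data procedures and statistical methods agreed", so that such decisions "cannot be influenced by the trial results". After that, "Partially unblinded analyses will then be presented with the two trial groups labelled by letters". Sections 4.4, 4.12 and 7 keep the allocation from the evaluation team and out of the research databases; the independent statistician holds the code. "The data analysis plan will be published prior to the end of recruitment".

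**The concern.** There are two difficulties, and the first carries the weight.

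First, observed imbalance is a poor basis for choosing covariates after a restricted randomisation. Restriction makes the four variables less likely to look imbalanced than they would under simple allocation. A choice driven by imbalance therefore tends to pass over the variables that the design itself treats as predictors. If they do predict the cluster means, an unadjusted analysis still counts their between-cluster variation as error, although the allocation has already removed much of it from the comparison. The standard error is then too large on average, the t test rejects too rarely under the null, and the interval is wider than it need be.

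Second, a random X/Y split carries no information on how the true arms differ. The protocol gives nobody the task of examining true-arm baseline balance without outcomes in view. An imbalance-based choice therefore sits badly with the aim of settling methods before results can influence them.

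**Working it through.** **Inputs.** 15 clusters, 8 v 7 (sections 2 and 4.4); 100 children assessed per cluster; effect 0.25 at ICC 0.01 and 0.40 at ICC 0.04, each with 90% power (section 4.10); best 20% of allocation schemes on four variables (section 4.4). Two-sided 5% is assumed. R2, the share of true between-cluster variance explained by baseline, is not in the documents. Baseline CREDI comes from other children (section 4.3.3), so it can act only through cluster means; the range 0 to 0.5 is shown.

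**1. The protocol's own figure.** Variance of a cluster mean = ICC + (1 - ICC)/100, which is 0.0199 at ICC 0.01 and 0.0496 at ICC 0.04.

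- 7 v 7 clusters, normal reference: SE = sqrt(0.0199 × 2/7) = 0.0754; 0.25/0.0754 = 3.316; power = Φ(3.316 - 1.96) = 91.2%. The same steps at ICC 0.04 give 91.9%. Both agree with the stated 90% to within 2 points.
- 8 v 7 clusters, t on 13 df: SE = sqrt(0.0199 × (1/8 + 1/7)) = 0.0730 gives 88.5%; SE = 0.1153 at ICC 0.04 gives 89.3%.

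**2. Size of the restricted set.** C(15,8) = 6,435 schemes; 20% = 1,287.

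**3. What adjustment can gain.** Adjusting for CREDI lowers the variance to ICC × (1 - R2) + (1 - ICC)/100. At R2 = 0.5 this is 0.0149 (ICC 0.01) or 0.0296 (ICC 0.04). With t critical values 2.179 (12 df) and 2.160 (13 df), the ratio of interval widths is sqrt(0.0149/0.0199) × 2.179/2.160 = 0.87, or sqrt(0.0296/0.0496) × 2.179/2.160 = 0.78. The interval is about 13% or 22% narrower. At R2 = 0 it is 1 to 2% wider.

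**4. Simulation under the restricted allocation.** Cluster means, CREDI the only driver, 40,000 replicates per cell. The size column is for the unadjusted t test on 13 df; the adjusted analysis uses 12 df.

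| ICC, effect | R2 | Size, unadjusted | Power, unadjusted | Power, CREDI-adjusted |
|---|---|---|---|---|
| 0.01, 0.25 | 0 | 4.9% | 88.6% | 87.5% |
| | 0.1 | 4.6% | 88.9% | 89.1% |
| | 0.3 | 3.8% | 89.6% | 92.4% |
| | 0.5 | 3.2% | 90.4% | 94.9% |
| 0.04, 0.40 | 0 | 5.1% | 89.2% | 88.3% |
| | 0.1 | 4.5% | 89.5% | 90.4% |
| | 0.3 | 3.4% | 90.9% | 94.9% |
| | 0.5 | 2.1% | 91.9% | 98.2% |

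The adjusted test has size 4.8 to 5.2% throughout.

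**5. How often the four variables would look imbalanced.** Section 4.11 gives no threshold, so these are illustrations only. At least one variable is flagged in 0% of restricted allocations at cluster-level p < 0.05, in 23% at a difference above 0.5 between-cluster SD, and in 92% above 0.25 SD. Whether the design variables enter the model thus turns almost wholly on the threshold.

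**6. The sham stage.** With the 0.25 SD threshold, the variables flagged under a random X/Y split were exactly those flagged under the true restricted allocation in only about 4% of runs.

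**The case against.** The strongest reply is that covariate selection belongs in the analysis plan. That plan is due before recruitment ends, and so before either primary outcome can be measured (ages 18-20 and 30-32 months). The sentence in 4.11 names no test or threshold, and a prespecified covariate set also adjusts for imbalance. This stands in part: the lack of a covariate list is not the point and is not raised. What remains is that the protocol names observed imbalance as the basis, and that basis suits a restricted design poorly.

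A reader might infer more than the documents support:

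- **That the rule cannot be applied, or that the covariates stay open until results are seen.** The statistician who holds the code could compare baseline variables between true arms without outcomes. A rule can be agreed blind and applied mechanically later, and the analysis plan can fix the covariates outright. The protocol assigns none of these steps to balance checking, but it prevents none of them.
- **That the restriction variables would never be adjusted for.** At 0.25 SD at least one is flagged in 92% of allocations. The 0% figure belongs to one possible threshold.
- **That the trial is underpowered or its type I error inflated.** Unadjusted power stays near 90%, and with a t reference any departure in size is downwards. A normal reference would give about 7% at R2 = 0, but that concerns degrees of freedom, and 4.11 names no reference distribution.

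It is also fair to say that the gain is conditional. At R2 = 0.1 and ICC 0.01, power moves only from 88.9 to 89.1%. If R2 = 0.5 is spread evenly over four uncorrelated variables, CREDI alone moves it from 90.1 to 90.5% (ICC 0.01) or from 92.0 to 93.2% (ICC 0.04).

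**Conclusion.** The point holds as a matter of method: the stated basis for adjustment should be changed, and the cost of leaving it is precision forgone, not invalid inference. With CREDI the only driver, R2 between 0 and 0.5 and t inference, an unadjusted analysis has size from about 5% down to 3% (ICC 0.01) or 2% (ICC 0.04). The change in power from adjusting for CREDI runs from -1 to +4.5 points, or from -1 to +6 points. These figures rest on an assumed R2, on analysis of cluster means with equal cluster sizes, and on the 20% rule without the separate caps in section 4.4.

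The sequencing point is secondary. A sham split cannot inform a choice that depends on true-arm imbalance, and the protocol assigns no outcome-free check. That is an awkward fit with the aim of section 4.11, but the statistician holding the code or the analysis plan could resolve it.

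**What to change.** In section 4.11, replace the reference to imbalances between arms with adjustment fixed in advance and made whatever the observed balance. The minimum is the cluster-mean baseline CREDI z-score used in the randomisation, the one variable that 4.4 always retains. Take inference from t with cluster-based degrees of freedom (15 - 3 = 12), and report the unadjusted result alongside.

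This is a change of wording; baseline CREDI is already collected. It costs about 1 point of power if CREDI is not prognostic, and it gains little if prognosis is spread over the four variables.

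Two extensions can be settled in the analysis plan before true groups are shown:

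- **All four variables (9 df).** Power is 91.6% (ICC 0.01) and 96.4% (ICC 0.04) in the spread case at R2 = 0.5, but about 6 points are lost if none is prognostic (82.6 v 88.6%; 83.2 v 89.2%).
- **A CREDI-adjusted permutation test over the retained schemes.** In the spread case size is 4.9 and 4.8% with power 92.0 and 95.0%; it costs 2 to 3 points if nothing is prognostic (85.7 v 88.5%; 86.9 v 89.3%).

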4.12 Blinding

Although the nature of the intervention precludes formal masking of fieldworkers during data collection, we believe that this is unlikely to lead to bias for the following reasons: the data collection will be carried out completely independently of the campaign team; emphasis throughout training will be on understanding early child development, rather than on evaluating the radio campaign; the assessments will follow standardized data collection protocols; and the coders of the responsive parenting videos will be blind to their allocation status. In addition, the strict “blinding” procedures for data analysis described in Section 4.11 have been designed to avoid any bias in methodological decisions or interpretation of findings all analyses will first be conducted blind to intervention allocation as. Finally, the randomisation will be carried out and the code held by the independent trial statistician; it will only be shared with campaign team.

4.13 Methods for protecting against bias

Methods for protecting against bias include:

1. Selecting FM radio stations for the trial with geographically distinct catchment areas, minimising the risk of contamination between clusters. Regular process data collection will also monitor this.
2. Using restricted randomisation to maximise comparability between intervention and control clusters at baseline with respect to radio exposure and key predictors of ECD.
3. Recruiting all eligible infants living in trial clusters to avoid selection bias and increase generalisability.
4. Range of quality control procedures to ensure data accuracy: cultural adaptation of instruments, pre-testing, establishing inter-rater reliability, range and consistency checks etc.
5. Regular visits to trial families to minimize loss to follow-up.

5. Process evaluation

5.1 Tracking and post-broadcast feedback

Independent radio trackers will determine if spots were broadcast as planned. Post-broadcast feedback on the campaign will be obtained through periodic focus group discussions (FGDs) and semi-structured key informant interviews. These data will be collected from at least two different communities every quarter, throughout the campaign duration. The objective is to find out whether the target audience have heard and understood the campaign messages, their reactions to them and whether there are any remaining barriers to behavioural change.

Message briefs and creative content can then be revised based on these findings, allowing continual iteration and adaptation of the campaign. These procedures are part of the standard DMI campaign methodology.

5.2 Surveillance monitoring data

Monitoring data on radio coverage will be collected every 3 months from trial mothers including listenership in the past week and questions concerning child health advice heard on the radio. These data will also be collected from a separate **monitoring cohort** of mothers who participated in the baseline survey together with 6-monthly questions on key behaviours & knowledge targeted by the campaign (to be designed in early 2022). These mothers will be followed for the first 18 months of the campaign. As they participated in the baseline survey, they will have older children; data collected from them will therefore allow the trial monitoring committees to make an early assessment of whether the campaign appears to be changing parental caring behaviours across the whole target age range of the first 3 years of life, as well as providing valuable feedback to the campaign.

5.3 Qualitative research

Acceptability will be measured through 25-30 qualitative interviews with caregivers, who will be asked about their experience and views on the intervention approach and content. Data from the post-production feedback research will also be utilized. The mechanisms and

barriers to behavioural uptake will be explored through qualitative interviews with a further sample of 25-30 families. Approximately five intervention communities will be selected to reflect the diversity within the study areas. Within communities' respondents will be selected to give diversity in key characteristics such as parity and socio-economic status. The sample sizes have been estimated for planning purposes, but the actual sample size will be based on the concept of saturation sampling, that is, we will continue investigating until no new information is elucidated.

The qualitative data around acceptability and mechanisms will be collected by trained interviewers who will use semi-structured guides. We will include non-direct questioning where caregivers narrate how they interact with their child followed by direct questions on exposure to the spots, their impact and an exploration of the potential intervention mechanisms. Guides will be translated into local languages and pretested through role plays and pilot interviews with respondents. Interviewers will take field notes during the interviews, which will then be written up, as well as tape-recording the interviews. Interviewers will meet regularly to discuss their findings and supervisors will read transcripts and give feedback on interviewer technique and content. Analysis will begin through the identification of themes during daily debriefing sessions. Key analytical categories will then be identified, and the interviews systematically indexed into the categories and interpreted and written up. Data quality will be ensured by in depth training of interviewers, pre-testing guides, encouraging reflexivity during data collection and the provision of feedback by supervisors on each interview transcript. During analysis consensus coding methods will be used for initial interviews.

6. Economic evaluation

The cost and affordability of programmes to stimulate nurturing care are crucial elements of the pathway to successful scale-up (18). However, the multi-sectoral nature of ECD programming has challenged the measurement of program costs and benefits, particularly in low-and middle-income country settings (39). In the absence of primary data, modelling techniques have been used to estimate the economic benefits of intervening in the first years of life (3) including long term effects (40). However, few studies in low-income settings have generated primary cost effectiveness and cost benefit ratios to aid national priority setting and improve program uptake (39).

SUNRISE offers the opportunity to fully cost, from the provider perspective, a large-scale intervention to promote ECD. These provider costs will be used to calculate a range of incremental cost effectiveness ratios including cost per beneficiary and cost per unit of cognitive gain. The full provider costing will then form the basis for affordability estimates calculated as a percentage of national gross domestic product. The cost of a fully-scaled programme will also be compared with current health and education spending in context. Simple modelling of the gains from improved early childhood stimulation, using estimates from the Lancet Series in Early Child Development (4), would then be used to conduct a fiscal space analysis to explore the expansion in national income likely to arise from the effects of the program, and what percentage of that growth in income the program cost constitutes. Finally, the equity impact of this intervention will be measured, as early child development interventions are known to attenuate the effects of poverty (2,41).

7. Data Management – Protection & Confidentiality

Data protection and confidentiality procedures will be specified and followed, in keeping with Good Clinical Practice (GCP) and the General Data Protection Regulation 2018. We plan to use REDCap for data collection which is a secure web application for building and managing online surveys and databases; REDCap is 21 CFR Part 11, FISMA, HIPAA, and GDPR compliant. All data (including video observations) will be collected on secure, password protected handheld tablets within an encrypted database, with the data transferred daily to a secure password protected cloud server, managed by IPA in Ouagadougou. All electronic data will be backed up locally on a weekly basis on encrypted external hard drives and stored off-site in Ouagadougou. Encrypted transfer of pseudonymized quantitative data to LSHTM will take place monthly via secure internet connection to a GCP-compliant LSHTM database, which allows full auditing of all data input and edits. Qualitative interviews will be audio-recorded on digital audio recorders.

As video and audio data cannot be de-identified, transfer of this material to the UK will be done through UCL's Data Safe Haven, which is a dedicated highly secure system for storing and handling sensitive data. The Data Safe Haven has been certified to the ISO27001 information security standard and conforms to the NHS Information Governance Toolkit. The Data Safe Haven is built using a walled garden approach, where the data is stored, processed and managed within the security of the system, avoiding the complexity of assured end point encryption. Video recordings will be viewed only by members of the SUNRISE team and for the purposes of the research, unless further explicit written consent is obtained.

Data concerning cluster allocation will not be stored in the local or LSHTM research databases, but held separately by the trial statistician in a secure password protected file.

8. Post-trial Data Access and Sharing

A final data sharing plan will be agreed between the study team, sponsor, Research Ethics Committee and funder and published before data collection is complete. The study's data sharing policy will be made accessible on the study website at LSHTM, on LSHTM's data repository, on the study's ClinicalTrials.gov record and on the Figshare repository (see below). All accessible data sources will be anonymised at the individual participant, family and cluster level. No identifiable data will be made publicly available. All data will be stored in accordance with GDPR regulations for research and in line with recognised data security standards (MRC, Wellcome, LSHTM and UCL policies).

The fully anonymised study dataset (with newly generated IDs, and appropriate consents in place), alongside codebooks and a detailed dataset guide, will be made available after 3 years of study completion and placed on LSHTM's Data Compass repository, a curated repository of research data and other reusable outputs produced by LSHTM and its collaborators. The data will also be mirrored on Figshare (<http://www.figshare.com>), a widely used online repository where users can make research outputs available in a shareable and discoverable manner.

All published papers will include links to the repository, with access to the relevant analytic data sets and analysis scripts, to ensure transparency and reproducibility. The datasets will be assigned unique DataCite DOIs. Video data and qualitative interviews, where anonymization is either not possible or there is a high risk of individuals being identified, will not be made

available in the repository. However, suitably qualified researchers will be able to access these data under strict collaboration agreements. Data access will be overseen by a committee composed of the PIs and at least one independent member. Access requests will be reviewed by the committee and recorded, with individual data sharing agreements signed by the data requester and his/her institution prior to data release. All variables will be labelled using a pre-defined naming convention and data and metadata catalogues will be produced to support data sharing. The catalogues and metadata will be listed on the LSHTM repository, the clinicaltrials.gov record and the Figshare entry. Personally-identifying data will be held for 10 years after the study is complete and then securely destroyed. Anonymized data will be curated and made available for public access 3 years after the study is complete.

Broadcast content sharing: DMI will make all the SUNRISE radio spots available for broadcast free of charge when intended to be used for public health purposes and not for commercial gain.

9. Trial monitoring

